#### 7.5.2 Form of the distribution of persistence and impact of covariates

Analysis of the persistence distributions usually relies on standard two-parameter distributions, particularly Weibull, Gamma, and Log-logistic, and their 3-parameter generalisations. These parametric curves will be approximated by a piece-wise constant hazard  $\mu(d,\theta)$  during each time interval d, which gives us the cumulative distribution function (probability that the duration is  $\leq d$ ):

$$F(d,\theta) = 1 - \exp\left(-\sum_{u=1}^{\infty} \mu(u,\theta)\right)$$

In considering the appropriate form of these distributions, it is important to appreciate that the observed between-individual variation in duration of IgM reflects not only the stochastic uncertainty in how a single survival distribution is realized, but also between-individual variation in survival distributions, due to variation in the inoculum and variation in immune response. To better account for this, semi-parametric functions may also be fitted; for example, a random walk smoothing process applied to  $log \, \mu(d)$ 

The impact of covariates on persistence will be assessed, including: presence of symptoms, coinfection, and previous infection with the same or other arboviruses. Avidity tests will be used to determine whether an infection is primary or secondary.

A common strategy to study covariates is proportional hazards (PH), which introduces a single additional parameter  $\delta_X$  for each covariate X to the log hazard. Thus, in the presence of the covariate,  $\mu(d,\theta)$  is replaced by  $\mu(d,\theta)\,e^{\delta_X}$ . Otherwise, if PH is counter-indicated by the data, it can be relaxed and interactions between the covariate and time since infection can be introduced. The alternatives can be evaluated by residual analysis and global goodness of fit.

#### 7.5.3 Estimating the persistence distributions of multiple tests

The ZIKA-VT protocol provides for

Author: [name] (UNIVBRIS)

23

- (i) PCR, IgM, and IgG tests on women with symptoms,
- (ii) PCR on all IgM+, IgG seroconversions, and rises in IgG titer.
- (iii) Repeat PCR, IgM, and IgG tests at the prescribed intervals until a first PCR-, IgM-, IgG falling titer, respectively.
- (iv) Use of serum, saliva, and urine samples.
- (v) Avidity tests may be used to determine if an infection is primary or secondary; this also carries information on timing of infection

Thus, each woman's record is likely to consist of a series of results on at least three tests and possibly more if more than one assay of each type is used.

The analysis above for a single test is readily extended to two or more tests k=1,2...K. The data on each individual i now consists of K sets of implied -++- sequences denoted  $U_{Li_k}, U_{Ri_k}, W_{Li_k}, W_{Ri_k}$ , and the parameter set is expanded to accommodate K distributions  $F_k(d,\theta_k)$ . The likelihood for the persistence tests for woman i is then:

$$\Pr\left(\begin{array}{c} (U_{Li_{k}}, U_{Ri_{k}}, W_{Li_{k}}, W_{Ri_{k}}) \mid \pi_{i}(t), \theta_{k} \end{array}\right) = \sum_{t} \pi_{i}(t) \prod_{k} \left( F_{k}(W_{Ri_{k}} - t - 1, \theta_{k}) - F_{k}(W_{Li_{k}} - t - 1, \theta_{k}) \right) \quad Max_{k}(U_{Li_{k}}) \leq t \leq Min_{k}(U_{Ri_{k}})$$

Note that, in this framework, the date of symptoms and the dates of short persistence tests such as PCR, are highly informative about the persistence distributions of longer persistence tests such as IgM and rising IgG.

Extension to multiple tests, use of a variety of tests, and changes in which tests are used, raises questions about the numbers of parameters that may need to be estimated. Our initial strategy will be to assume that the persistence distributions of all tests of the same type (PCR, IgM, rising IgG) have the same underlying parametric or semi-parametric form, with persistence distributions that differ only by a single parameter, for example based on a proportional hazards assumption. This constant would be estimated from the data. Persistence distributions for different *samples* (serum, saliva, urine) on the same test will be treated the same way.

These are strong assumptions, but ones which minimize the number of additional parameters, and which will allow for quite precise estimation of persistence in large datasets. They will be rigorously tested by goodness of fit and residual analyses, and sensitivity analyses will be conducted to establish their impact on results.

## 7.6 Accounting for imperfect test sensitivity and specificity, and cross-reactivity

As noted earlier, we need to calculate for each woman recruited into ZIKA-VT, the probability that she was infected in pregnancy, and the distribution of GA when this infection occurred, if it occurred at all, based on tests with imperfect accuracy.

Author: [name] (UNIVBRIS)

24

For example, a sequence of four ZIKV IgM- results throughout pregnancy, assuming there were no IgG, PCR tests and no symptoms, would be scored as "No evidence of maternal infection in pregnancy" in basic analyses, but there is a possibility that they are all false -ves.

As long as the testing algorithm is relatively sensitive, say 95% or more, the bias in estimates of the vertical transmission due to false -ves is likely to be negligible. A small proportion (<5%) of maternal infections would be missed from the denominator, but their babies will not be followed up, and so would also be missed from the numerator. The exception to this would be if they are not only congenitally infected but their congenital infection is apparent. But it can be shown that, on current evidence, this would lead to only a very slight over-estimation of the VTR.

The difficulties posed by false *positive* IgM tests are, however, far more serious. If the specificity of an IgM test is 95%, then 5% of uninfected mothers will receive false +ve results, and will be considered infected in pregnancy. If 10% of women are infected in pregnancy, then, for every 15 women considered as infected in pregnancy, only (approximately) 10 would be truly infected, and the vertical infection rate will be underestimated by a factor of 1.5. If incidence is lower, and only 1% of women are infected in pregnancy, then only 1 in 5 women being followed are truly infected and the vertical transmission rate will be underestimated by a factor of 5.

The diagnostic algorithm will include confirmatory tests, and it is hoped that the effective specificity and sensitivity of the entire algorithm will be high. However, it may still be necessary to take false positives and negatives into account. Calculations capable of making these adjustments (see Appendix 2) assume that an estimate is available of the absolute a priori risk of infection, based on surveillance data. This is in contrast with the calculations in Section 7.4 which assumed perfect test accuracy, where only the relative probabilities were needed. The reason for this is that the probability that a ZIKV IgM+ is a false positive will be much higher if there is very little ZIKV circulating at the time, and much greater – depending on the cross-reactivity of the test – if there is a high incidence of DENV. Methods for obtaining information on the absolute incidence are explained in Section 8.1.7).

Note that adjustments for sensitivity and specificity need to be based on the properties of the entire algorithm, and on the entire set of results through the pregnancy.

#### 7.7 How the full analysis will be used

The various components discussed above can be assembled into a single analysis, as shown by the influence diagram (*Figure 1*), providing a single integrated analysis of: test persistence and its covariates; GA at maternal infection; VTR and its risk factors; and risk of severe congenital outcomes and its risk factors.

One of the outputs will be the distribution of maternal GA at infection, in weeks. We will extract the posterior mean probability that a maternal infection occurred during each month, or trimester, and take this forward to be used in analyses along the lines of Tables 3 and 4. In effect the 0,1 "dummy covariates" that would be used in conventional analyses of GA at infection as a risk factor, can then be replaced by a set of probabilities. Note that these cannot exceed one, but they need not add to one, if there is a finite probability that the infection occurred before, or after, pregnancy. Standard

Author: [name] (UNIVBRIS)

25

statistical software can then be used to explore GA at infection as a risk factor, or interactions between GA at age of infection and other risk factors, exactly as if 0,1 covariates were being used.

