#### 7.1 Vertical transmission rate

Assume that for each woman i we will have estimates of the probability  $\pi_i(t)$  that the onset of her infection occurred in week t. We assume that vertical transmission can only occur if infection exists during pregnancy, so that the *onset* is in the interval  $-2 \le t \le G_i$  where  $G_i$  is the gestational age at delivery. If the probability of vertical transmission given maternal infection at week t is V(t), then the probability of in utero transmission in women i is:

$$v_i = \sum_t V(t)\pi_i(t), \quad Y_i \sim Bern(v_i)$$
(7.1)

The outcome data  $Y_i=0,1$  (1 indicating Vertical infection (VI), 0 indicating no VI in a child born to women i), is a Bernoulli realization of the parameter  $v_i$ . In a Bayesian framework, we can attribute a vague prior to V(t) and use the data obtain posterior distributions for V(t),  $v_i$ , and  $\pi_i(t)$  given the Bernoulli likelihood.

In practice, a smooth parametric or semi-parametric function would be fitted to V(t). The analysis is readily extended to include additional risk factors  $\mathbf{X}_i$  with coefficients  $\boldsymbol{\beta}$ :

$$logit(v_i) = logit(\sum_t V(t)\pi_i(t)) + \boldsymbol{\beta}^T \mathbf{X}_i$$

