#### 7.2 Risk of severe outcomes of congenital infection

A similar form of analysis will be carried out for severe outcomes of congenital infection. The precise definition remains to be determined, but could include: fetal death, stillbirth, microcephaly, cranial disproportion, or ZIKV-related death within the first two years. The analysis will estimate the risk of severe outcomes conditional on vertical transmission having taken place. This clarifies that there may be two distinct processes: risk factors for congenital infection, and risk factors for severe damage given congenital infection.

The form of analysis for severe clinical outcomes conditional on vertical infection parallels that for vertical transmission rate. Here,  $c_i$  is the risk of severe outcomes in a child born to women i, and C(t) is the probability of severe outcomes given maternal infection in week t. Data  $Z_i=0,1$  indicating severe (1) or non-severe (0) outcomes is a Bernoulli realization of  $c_i$ , and can be used to update C(t) and  $\pi_i(t)$ :

$$c_i = \sum_t C(t)\pi_i(t), \quad Z_i \sim Bern(c_i)$$

Author: [name] (UNIVBRIS)

19

The analysis can be extended to include risk factors as shown above.

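### SAP 7.7 carries trimester probabilities already updated by the severe outcome into the Table 3 and 4 regressions, which distorts timing effects for outcomes in, or correlated with, that severe outcome

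*SAP*

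**What the plan says.** Section 7.1 models vertical infection Y_i as Bernoulli with probability Σ V(t)π_i(t). It lists π_i(t), with V(t) and v_i, among the quantities that receive a posterior from these data.

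Section 7.2 does the same for the severe outcome Z_i, conditional on vertical infection. Z_i "can be used to update C(t) and" π_i(t). The definition of Z is still open, but the candidates are "fetal death, stillbirth, microcephaly, cranial disproportion, or ZIKV-related death within the first two years".

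Section 7.4.6 confines the timing of maternal infection to pregnancy when the infant is infected, and 7.5.1 does the same in the persistence likelihood.

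Section 7.7 assembles these parts, "providing a single integrated analysis of: test persistence and its covariates; GA at maternal infection; VTR and its risk factors", together with the risk of severe congenital outcomes. On the timing output it then says: "We will extract the posterior mean probability that a maternal infection occurred during each month, or trimester, and take this forward" to the Table 3 and 4 analyses, where the probabilities enter standard software "exactly as if 0,1 covariates were being used".

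Tables 3 and 4 list fetal deaths, deaths at one year, head circumference, severe malformations and severe clinical outcomes, which overlap the candidates for Z. Section 6 calls these analyses hypothesis-forming.

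**The concern.** Replacing an unknown trimester by its expectation given tests, symptoms and surveillance is ordinary regression calibration, and is sound in a linear model. Replacing it by its expectation given those data and the outcome, and then regressing the same outcome on it, uses the outcome twice. C(t) is estimated under a vague prior, so chance differences between trimesters are fed back into the women's timing and then appear as timing effects in the second stage. Treating the probabilities as known covariates also drops the uncertainty in the dating.

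Gestational age at infection is the central risk factor in the objectives (2.1). A procedure that produces timing effects where none exist, or magnifies real ones, would misdirect the hypotheses that Tables 3 and 4 are meant to form.

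**Working it through.** The SAP gives no figure to reproduce, and section 10.3 states that no formal sample size calculation was made. The risks, sample sizes and dating precision below are assumptions, except n = 1000, which is the section 10.3 target for infected women.

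**One woman.** Bayes' rule applied to the 7.2 model gives P(trimester j | Z=1) = π_j C_j / Σ π_k C_k, and the same with 1−C for Z=0. Take π = (1/3, 1/3, 1/3) and C = (0.30, 0.20, 0.10).
- Z=1: denominator 0.20, giving (0.50, 0.33, 0.17).
- Z=0: denominator 0.80, giving (0.29, 0.33, 0.38).

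Two women with identical tests now have different covariates solely because of the outcome.

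**Two periods.** Assumptions: 300 vertically infected infants, pre-outcome P(trimester 1) ~ Beta(2,2), uniform priors on C, analysed outcome equal to Z, nobody dated by symptoms, linear regression of Z on the exported probability.
- No timing effect (20% v 20%): repeat runs reject at nominal 5% in 68 to 73% of replicates, against 3 to 7.5% with outcome-free probabilities.
- True risks 40% v 10% (difference 0.30): mean estimate 0.96 to 0.99, against 0.30 to 0.31 with outcome-free probabilities. The joint model's own C difference is 0.28.

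**Three trimesters.** Dating is Dirichlet with concentration 0.3, 1 or 3 (mean largest probability 0.77, 0.61, 0.50), C has Beta(1,1) priors, and the regression test has 2 degrees of freedom.

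| | conc. 0.3 | conc. 1 | conc. 3 |
|---|---|---|---|
| Null (20% throughout), n=200: rejection | 44% | 81% | 94% |
| Null, n=1000: rejection | 41% | 84% | 99% |
| True T1−T3 = 0.20, n=200: estimate | 0.35 | 0.57 | 0.78 |
| True T1−T3 = 0.20, n=1000: estimate | 0.37 | 0.68 | not run |

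With feedback cut, null rejection is 4 to 7% and the mean estimate is 0.20. The inflation runs from 0.354/0.20 = 1.8 to 0.777/0.20 = 3.9 times. Vaguer dating makes it worse, and a larger sample does not cure it. Under the null the false effect averages near zero. The joint model's C1−C3 is not inflated: 0.19 to 0.20 at n=1000, and 0.12 to 0.19 (shrunk) at n=200.

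**Outcomes other than Z** (n=200, concentration 1, null). At correlations of 0, 0.2, 0.4 and 0.7 with Z, rejection is 3.5%, 10.5%, 32% and 66%.

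**Symptom-dated women** (two-period design). If 20% or 50% are dated exactly, null rejection is 52% or 28%, and a true 0.30 is estimated as 0.69 or 0.45.

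**Conditioning on Y.** Within the vertically infected rows Y=1 for everyone, so conditioning on it is not circular. Removing it there does harm when transmission depends on timing. With V = 50% v 10% and a true risk difference of 0.30, calibrated timing is 0.5p/(0.5p + 0.1(1−p)). Its regression slope on the unconditioned p, over Beta(2,2) reweighted by 0.1 + 0.4p, is 0.61. The estimate is therefore 0.61 × 0.30 = 0.18, whereas Y-conditioned probabilities give 0.29 to 0.30. With V = 40% v 20% the slope is 0.91 and the estimate 0.27.

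**Section 7.4.6 when mothers are pooled.** Take one IgM+ at week 6 with flat timing over the preceding D weeks. P(trimester 1) is 9/13 = 0.69 for D=12 and 9/27 = 0.33 for D=26. It becomes 1.00 in both cases solely because the infant is infected.

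**The case against.** The strongest objection concerns what π_i(t) is. In 7.4.1 and 7.4.2 it is fixed by symptom or test dates. In 7.4.4 and 7.4.5 it is a function of test dates and shared persistence and surveillance parameters. In 7.4.3 it is Dirichlet with surveillance counts. If only that quantity is exported, one infant's result barely moves it. In the two-period design, with an assumed total count of 10, 50 or 200, null rejection is 15%, 8.5% or 5.5% (5% with feedback cut), and a true 0.30 is estimated as 0.41, 0.33 or 0.31. This stands as a possible reading. The SAP does not commit to it: 7.1 and 7.2 say the outcomes update π_i(t), 7.4.6 conditions on the infant directly, and 7.7 exports a posterior from the joint model. I could not see the drawing of Figure 1; its caption mentions no cut.

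Two further objections limit the consequence. The two fundamental outcomes in section 10.4 are estimated inside the joint model. Tables 3 and 4 are labelled hypothesis-forming, which lowers the stakes but does not remove the bias.

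A reader might infer that every Table 3 and 4 outcome is regressed on itself. The documents do not support that: Z is not finally defined, 7.2 fits it only among the vertically infected, and Table 4 also covers outcomes such as birthweight, length and auditory findings, which are affected only as far as they correlate with Z or Y. Nor does it follow that all feedback from Y should be removed; within rows split by vertical infection that would introduce bias.

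**Conclusion.** The point holds with limits. As written, 7.7 allows the severe outcome to shape the timing covariate against which it, or a correlated outcome, is then tested. If each woman's posterior trimester given all data is exported, the result is excess false-positive timing effects of random sign and exaggerated true effects. Null rejection is about 70% in the two-period design, and 41 to 99% in the three-trimester design depending on dating precision. These figures assume that the outcome equals Z and that nobody is dated by symptoms, and they fall as either assumption is relaxed. If only the 7.4 function of test dates and shared parameters is exported, the distortion is much smaller. Outcomes independent of Z and Y are unaffected, as are V(t) and C(t) from the joint model. This is a should-fix point.

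**What to change.** - State in 7.7 exactly which quantity is exported.
- For Tables 3 and 4, use timing probabilities that exclude the analysed outcome, by cutting the feedback from Z.
- Keep conditioning on Y, and the 7.4.6 restriction, within rows stratified by vertical infection. Drop both only where all infected mothers are pooled and vertical infection is the outcome or is correlated with it.
- Alternatively, estimate these outcomes inside the joint model.
- Propagate timing uncertainty, by bootstrap with the outcome-free probabilities, or by analysing repeated posterior draws of the trimester (not posterior means) from a model that contains the analysed outcome.
- Delete the statement that the probabilities can be used "exactly as if 0,1 covariates were being used".

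The cost is one additional model run, a revision of the SAP wording, and somewhat wider intervals.

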# 6. Vertical transmission risk and outcomes: basic statistical outputs

Basic analyses, without attempts to correct for sensitivity, specificity and cross-reactivity, and making only the simplest assumptions about test persistence, are set out as a series of table shells. The most likely trimester of maternal infection in these tables would be derived from rules based on dates of tests and assumptions about test persistence.

Table 1 provides crude estimates of the risk of vertical transmission and the risk of congenital anomalies, by most likely trimester of presumed maternal infection, and by symptoms.

Table 2 provides a simple listing of congenital anomalies.

Table 3 is a breakdown of outcomes of pregnancy (fetal death, stillbirth) by indicators of maternal infection in pregnancy.

Table 4 represents a generic form of analysis for delivery data and subsequent pediatric outcomes, separate for ZIKV, DENV, and CHIKV, and by trimester of infection, and laid out by birth cohort (Vertically infected, Maternal Infection but no vertical infection, No maternal infection). Covariates can be taken into account by multiple regression.

With so many outcomes to examine, in three distinct diseases, the Table 3 and Table 4 analyses must be considered as hypothesis-forming, not hypothesis-testing.

Tables 1-4 will be computed with standard software, such as SAS, STATA, or R. However, as pointed out in Section 5, any analyses involving the denominator for vertical infection, so especially Table 1 estimates, will be vulnerable to very considerable biases due to inaccuracy in identifying the timing of maternal infection, and indeed, whether there was a maternal infection during pregnancy at all.

The methods set out in the next section are designed to solve these problems, leading to gestational age at infection being represented as *probabilities* that infection occurred in the 1st, 2nd, and 3rd trimester, rather than the usual 0,1 "dummy covariates" used in conventional analyses of gestational age as a risk factor.

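### Section 7.7 lets trimester probabilities stand in for 0/1 dummies in any standard regression; this is right for identity-link models but not for logistic models of the binary Table 3 and 4 outcomes

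*SAP*

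**What the plan says.** Section 7.7 describes how the output of the integrated Bayesian analysis is used further: "We will extract the posterior mean probability that a maternal infection occurred during each month, or trimester". These values go forward: "take this forward to be used in analyses along the lines of Tables 3 and 4". There the usual trimester dummies "can then be replaced by a set of probabilities", and standard software may be used to explore gestational age at infection, alone or in interaction with other risk factors, "exactly as if 0,1 covariates were being used". The section adds that "they need not add to one, if there is a finite probability that the infection occurred before, or after, pregnancy". It gives no restriction by type of outcome or link function, and no sensitivity analysis.

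Tables 3 and 4 mix continuous outcomes (birthweight, length, head circumference, gestational age) with many binary ones (fetal death, preterm birth, neonatal death, small for gestational age, malformations, auditory and ophthalmological problems). Section 6 says of the Table 4 analyses only that "Covariates can be taken into account by multiple regression"; no link is named.

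Sections 7.1 and 7.2 treat the same uncertainty differently. There a woman's risk is the probability-weighted sum of the week-specific risks, v_i = Σ V(t)π_i(t) and c_i = Σ C(t)π_i(t). When risk factors are added in 7.1, the logit is taken after that averaging.

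**The concern.** If a woman's trimester of infection is uncertain, her risk is the average of the trimester risks, weighted by her probabilities. An identity-link model with those probabilities as covariates reproduces this exactly. A logistic model with the same covariates makes her log-odds the weighted average of the trimester log-odds, which is a different and, for the risks considered here, lower number. The fitted coefficients adjust to this misfit, so they are no longer the trimester log odds ratios.

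The error does not shrink with more data, and it depends on how precisely infection is dated. Section 4 requires estimates that are unbiased whatever the scheduling of laboratory tests, and says that this SAP delivers them. For binary outcomes analysed as Section 7.7 allows, that claim would fail. Interactions, which 7.7 invites, are exposed too: under 7.4.1 symptomatic women have an exact onset week while others are spread over an interval, so dating precision is tied to symptoms, one of the key risk factors in Section 2.1.

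**Working it through.** **Inputs.** From the SAP: the substitution rule (7.7), the risk-averaging form (7.1, 7.2), the spreading of probability over contiguous weeks (7.4), and a target of about 1000 infected women (10.3). The SAP states no figure on this point, so there is nothing to reproduce. All risks and dating patterns below are assumptions; Section 10.3 itself says there is no consensus on transmission or damage rates.

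**One woman, probability 0.5 in each of two trimesters.** Risk averaging gives 0.5·R_a + 0.5·R_b. Log-odds averaging gives expit(0.5·logit R_a + 0.5·logit R_b).
- Risks 30% and 10%: 20.0% against expit((−0.847 − 2.197)/2) = expit(−1.522) = 17.9%.
- Risks 10% and 5%: 7.5% against 7.1%.
- Risks 30% and 2%: 16.0% against 8.6%.

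**Large-sample limits.** Probabilities p_ik are generated so that P(Y_i=1) = Σ_k p_ik·r_k holds exactly, i.e. perfect calibration. The limit of a logistic regression on p_ik is compared with the true odds ratios (OR).

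*Infected women only, trimester 3 as reference.* Contiguous window containing the onset, onset uniform over 40 weeks, trimester cuts at 13 and 27 weeks:

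| Risks T1/T2/T3 | Window (weeks) | T1 OR, fitted (true) | T2 OR, fitted (true) | T2 ratio |
|---|---|---|---|---|
| 10/7/5% | 12 | 2.11 (2.11) | 1.44 (1.43) | 1.01 |
| 10/7/5% | 30 | 2.11 (2.11) | 1.50 (1.43) | 1.05 |
| 30/10/5% | 4 | 8.17 (8.14) | 2.16 (2.11) | 1.02 |
| 30/10/5% | 12 | 8.31 (8.14) | 2.30 (2.11) | 1.09 |
| 30/10/5% | 20 | 8.53 (8.14) | 2.62 (2.11) | 1.24 |
| 30/10/5% | 30 | 8.41 (8.14) | 3.04 (2.11) | 1.44 |
| 15/5/3% | 20 | 6.11 (5.71) | 2.14 (1.70) | 1.26 |
| 15/5/3% | 30 | 6.09 (5.71) | 2.47 (1.70) | 1.45 |

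If the probabilities are instead spread diffusely over all three trimesters (uniform Dirichlet), risks of 30/10/5% give ORs of 6.87 and 1.61. The direction is reversed.

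*Uninfected reference at 2%, diffuse (Dirichlet) probabilities that need not sum to one over the trimesters, risks 30/10/5%.* True ORs are 21.0, 5.44 and 2.58.
- Mean largest probability per woman 0.72: fitted 13.4, 3.08, 1.66, too small by factors of 1.56, 1.77, 1.56.
- Mean largest probability 0.52: fitted 13.0, 2.49, 1.45, factors 1.61, 2.18, 1.78.

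*No effect (2% throughout).* All fitted ORs are 1.00.

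*Identity link, same probabilities.* The true risk differences are recovered in every scenario tried.

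**Does risk averaging repair it?** With risks 2/30/10/3% (none/T1/T2/T3) and mean largest probability 0.72, the true ORs are 21.0, 5.44, 1.52. The Bernoulli likelihood with Σ p_ik·r_k gives 21.03, 5.45, 1.52; the 7.7 logistic fit gives 13.91, 3.16, 1.21. In 300 samples of 1000 women, the median ORs were 23.95, 5.73, 1.59 for risk averaging and 14.02, 3.21, 1.23 for the 7.7 approach.

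**Interaction.** Risks 30/10/5%, no symptom effect, half the women dated exactly and half by a window. The logistic fit shows a symptom × trimester 2 interaction OR of about 0.8 with 20-week windows and 0.7 with 30-week windows, where the truth is 1.

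**The case against.** The strongest reply is about scope. Section 7.7 does not name logistic regression, and its wording is permissive. Tables 3 and 4 are declared hypothesis-forming in Section 6, and Section 10.4 puts everything beyond the two fundamental outcomes under that heading. Those two outcomes, in 7.1 and 7.2, already average on the risk scale. All of this stands and limits the weight of the point. It does not rescue the sentence: logistic regression is the conventional choice for a binary outcome, the SAP uses logits in 7.1 and odds ratios in Table 7, and no caveat confines the statement to linear models.

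The second reply is that large errors need unusual inputs. This largely stands. Tests define an interval (5.3) and 7.4 spreads probability over contiguous weeks, so doubt will mostly lie between adjacent trimesters. With short windows or modest gradients the error is a few percent.

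Third, Section 10.2 speaks of survival analyses for categorical pediatric outcomes. The odds-ratio figures and a Bernoulli likelihood do not carry over to those directly. A log-hazard model is also non-linear, but its error was not computed.

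A reader might infer that trimester 1 effects are always understated, or that a gestational-age effect could appear where none exists. Neither follows. The direction changes with the dating pattern, and under no effect there is no bias. The spurious interaction above needs a true gradient together with unequal dating precision.

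**Conclusion.** Wrong as written, within a limited scope. The equivalence in Section 7.7 is exact for identity-link models and false for logistic or other non-linear-link models of binary Table 3 and 4 outcomes, where it also departs from the SAP's own 7.1 and 7.2. The gestational-age odds ratios are then inconsistent even with calibrated probabilities. Because "Note that these cannot exceed one, but they need not add to one", the same fault can arise between infection in pregnancy and the reference state. It does not arise there for the vertically infected cohort, which 7.4.6 restricts to infection during pregnancy.

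The figures in the working range from no error to a factor of about 2.2. They illustrate sensitivity to assumed risks and dating patterns and are not a forecast for this study. The documents do not support reading this as a fault in the vertical transmission rate or the severe-outcome analysis. It should be corrected because the stated rule is wrong, the remedy is cheap, and diffuse timing, where the error is largest, is what 7.7 was written to handle.

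**What to change.** In Section 7.7, confine the sentence on treating the probabilities like 0/1 covariates to identity-link models (means of continuous outcomes, risk differences). For binary outcomes, specify averaging on the risk scale:

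P(Y_i = 1) = Σ_k p_ik·r_k + (1 − Σ_k p_ik)·r_0,

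where k runs over trimesters (or months) and r_0 is the risk in the reference state. Say which way risk factors enter:
- the 7.1 form, logit of the averaged risk plus b'X_i; or
- inside each component, Σ_k p_ik·expit(a_k + b'X_i) + (1 − Σ_k p_ik)·expit(a_0 + b'X_i). State that this is a different model from 7.1.

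For any outcome analysed by survival methods under 10.2, say separately how uncertain timing enters.

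Cost: a short custom likelihood in place of an off-the-shelf logistic command, and a few changed lines in the SAP. At about 1000 women some upward small-sample bias in a large odds ratio remains (median 23.95 against 21.0 in the run above), less than the error it replaces (14.02).
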